4.9 Efficacy Analysis

A closed, hierarchical testing procedure will be used to control the overall false-positive rate at 5% (two-sided) for the primary comparison of dinutuximab + irinotecan versus irinotecan. The primary efficacy endpoint (Overall Survival) will be tested first and, if it achieves statistical significance, the secondary endpoints will be tested in the following sequence: PFS, ORR and CBR. All the analyses described below will be performed for the purpose of displaying summary statistics, but once the first in the sequence of tests yields a p-value that exceeds 0.05, the nominal p-value for this and subsequent endpoints in the series will be declared non-significant.

4.9.1 Overall Survival (OS)

OS is defined as duration of time from the date of randomization to the date of the subject's death from any cause. Subjects who are alive or permanently lost to follow-up at the cut-off date for the analysis will be censored at the last date the subject was known to be alive.

The primary analysis of OS will be performed in the ITT set using a stratified log-rank test (two-sided, $\alpha=0.05$) to evaluate the difference between survival curves for the dinutuximab combination group versus the irinotecan group. Stratification will be based on the same factor used for randomization, i.e., the subject's response to prior platinum therapy (relapse-free period during prior platinum treatment < 3 months vs. ≥ 3 months). Similarly, the stratified log-rank test will be used to compare OS for the dinutuximab combination group versus the topotecan group (an exploratory analysis, not part of the hierarchical procedure described above).

Median OS in each treatment group and the corresponding 2-sided 95% confidence interval (CI) will be estimated using the Kaplan-Meier method (Brookmeyer³, 1982). Kaplan-Meier curves for OS distributions will be plotted over time for each treatment group.

In addition, two-sided 95% CIs for the OS rate for each treatment will be constructed at pre-specified time intervals (i.e., 6 months, 12 months, ..., etc.), using the log-log transformation methodology of Kalbfleisch and Prentice (Kalbfleisch⁴, 1980) where the estimated variance of $\log(-\log(\hat{S}(t)))$ is:

$$\tau^2(t) = \sigma^2[\hat{S}(t)\log(\hat{S}(t))]^2$$

The 100 x (1- α)% CI for S(t) is given by:

$$\left[\hat{S}(t)\right]^{\exp(z_{\alpha/2}\tau(t))} \leq S(t) \leq \left[\hat{S}(t)\right]^{\exp(-z_{\alpha/2}\tau(t))}$$

Note that the stratified log-rank test will be used for evaluating the treatment difference. The Kaplan-Meier plots as well as the summary statistics for median OS and the OS rate will be derived from analyses without adjusting for the stratification factor.

The treatment effect of the dinutuximab combination on OS, as compared to irinotecan, will be estimated by the hazard ratio and its 95% CI; the Cox proportional hazards model will be used for this analysis, stratified by the subject's response to prior platinum therapy. Similarly, the hazard ratio and 95% CI comparing the dinutuximab combination group and the topotecan group will be provided.

Sensitivity analyses for the OS endpoint will include an analysis of subjects in the mITT and Per Protocol populations (as defined above). An additional sensitivity analysis will be performed that considers ITT subjects who were lost to follow as having died on their last follow-up date.

In addition, Cox proportional hazards model will be used to explore the potential impact of stratification factors and other baseline covariates on the primary OS endpoint. The potential influence of the following factors will be examined: age, gender, geographic region of enrolling site, ECOG status, duration of prior response to platinum, PD-L1 status (if available), and years since diagnosis. Candidate covariates for the multivariate model will be selected using a backward selection process and only variables significant at a 10% level will be considered for the final multivariate model.

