7.2.6 SAS[®] Procedures

This section provides sample SAS[®] code to illustrate statistical analyses specified in the statistical methods section. All computer output from SAS[®] statistical procedures serving as a basis for extracted results (e.g., LIFETEST) will be retained for quality control procedures and will be included in CSR appendices.

Exact 95% confidence interval on ORR/DCR:

```
proc freq;
  by trt;
  table resp / binomial;
run;
```

Median survival time and survival rates with 95% confidence intervals:

```
proc lifetest method=lt intervals =(0 to 24 by 6) outsurv=surv;
  time tte*censor(0);
  strata trt
run;
```

Note: 95% confidence intervals for time intervals (e.g., 3 months, 6 months) will be extracted from the data set SURV.

Cox proportional hazard ratio:

```
proc phreg data=kmvar;
  model aval*cnsr(1) = trtpn/rl;
  strata stln;
run;
```

Stratified log-rank test p-value:

```
Ods output HomTests=pval;  
proc lifetest data=kmvar;  
  time aval*cnsr(1);  
  strata stln / group = trtpn;  
run;
```

Additional SAS[®] code is provided, where necessary, in programming notes for table mock-ups.

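### SAP 4.9.1, as its text reads, multiplies by [S log S]² in the log-log variance for the OS-rate intervals where it must divide, and leaves σ² undefined

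*SAP*

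**What the plan says.** SAP 4.9.1 states that "two-sided 95% CIs for the OS rate for each treatment will be constructed". The planned times run in steps of 6 months. The method comes from a cited textbook and is described as "using the log-log transformation methodology". The SAP introduces the variance with "where the estimated variance of $\log(-\log(\hat{S}(t)))$ is" and then gives "\tau^2(t) = \sigma^2[\hat{S}(t)\log(\hat{S}(t))]^2". There is no division sign, and σ² is not defined. The interval that follows raises Ŝ(t) to the powers exp(+zτ) and exp(−zτ).

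SAP 7.2.6 gives sample code for median survival and survival rates: "proc lifetest method=lt intervals =(0 to 24 by 6) outsurv=surv". A note below it says that "95% confidence intervals for time intervals (e.g., 3 months, 6 months) will be extracted from the data set SURV". The section describes its code as a sample that illustrates analyses specified in the methods section.

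Protocol 10.9.1 gives no formula for this interval, and SAP 1 says the SAP's statistical text supersedes the protocol's. Nothing elsewhere in the two documents corrects the line.

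**The concern.** The interval expression in 4.9.1 is the right one for a log-log interval, but the τ supplied to it is not the standard error of log(−log S). Because |S log S| is always well below 1, multiplying by its square instead of dividing shrinks the standard error severely. An interval built that way would be labelled 95% and would cover the true OS rate far less often.

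At stake are the OS rates at fixed times, which are descriptive summaries of the primary endpoint that readers of a clinical study report look at. A programmer or quality-control reviewer checking output against 4.9.1 would also find a mismatch, with no stated rule for resolving it.

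**Working it through.** **1. Planning inputs (SAP 4.2).** The plan assumes HR 0.725, medians of 6 and 8.3 months, 184 subjects each in Groups A and B and 92 in Group C, 10 months of accrual and 14 months of further follow-up. The SAP states no interval width, so the only figure to reproduce is the power statement:

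- Events for 80% power (Schoenfeld): 4(1.960 + 0.842)²/(ln 0.725)² = 304.
- Power with 306 deaths: Φ(½√306 × 0.3216 − 1.960) = 80.3%.
- Exponential medians of 6 and 6/0.725 = 8.28 months give 162.4 + 145.4 = 307.8 expected deaths in Groups A and B.

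The planning inputs are consistent, so they can be used below. Exponential survival is an assumption, because the SAP gives no OS rates.

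**2. Direction of the error.** d/dS log(−log S) = 1/(S log S). By the delta method, Var[log(−log S)] = Var(S)/[S log S]².

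- If σ² = Var(S), the divisor is [S log S]².
- If σ² is the Greenwood sum Var(S)/S², the divisor is (log S)².

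Both usual readings divide. Neither gives the formula as it reads.

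**3. Size if σ² = Var(S).** Correct τ over stated τ is 1/(S log S)², whatever the sample size or censoring. |S log S| is largest at S = 1/e, so the ratio is never below e² = 7.39. It is at most 15 only for S between about 0.12 and 0.69.

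Worked case, Group A at 6 months, S = 0.50, n = 184, no censoring before t:

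- SE(S) = √(0.25/184) = 0.0369, and |S log S| = 0.3466.
- Dividing: τ = 0.0369/0.3466 = 0.1064, interval 0.426 to 0.570.
- As stated: τ = 0.0369 × 0.3466 = 0.0128, interval 0.491 to 0.509.

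All planned time points, n = 184 and S = 0.5^(t/median). The last two columns are ratios of interval widths, which differ slightly from the τ ratio because the back-transformation is not linear:

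| Group, month | S | Interval, dividing | Interval, as stated | Ratio, σ² = Var(S) | Ratio, Greenwood sum |
|---|---|---|---|---|---|
| A, 6 | 0.500 | 0.426–0.570 | 0.4913–0.5086 | 8.3 | 4.15 |
| A, 12 | 0.250 | 0.190–0.314 | 0.2425–0.2575 | 8.3 | 2.07 |
| A, 18 | 0.125 | 0.082–0.177 | 0.1218–0.1283 | 14.7 | 1.84 |
| A, 24 | 0.0625 | 0.034–0.104 | 0.0615–0.0636 | 33.4 | 2.09 |
| B, 6 | 0.605 | 0.530–0.671 | 0.5984–0.6115 | 10.8 | 6.53 |
| B, 12 | 0.366 | 0.297–0.435 | 0.3566–0.3754 | 7.35 | 2.69 |
| B, 18 | 0.221 | 0.165–0.284 | 0.2148–0.2282 | 8.9 | 1.98 |
| B, 24 | 0.134 | 0.090–0.187 | 0.1304–0.1376 | 13.7 | 1.84 |

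At 3 months, which the note in 7.2.6 names as an example, the ratios with σ² = Var(S) are 16.7 (A) and 26.3 (B).

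**4. Size if σ² is the Greenwood sum.** The τ ratio becomes 1/[S (log S)²]. At S = 0.50 this is 1/(0.5 × 0.4805) = 4.16. The width ratios are in the last column: 1.84 to 6.53 at 6 to 24 months.

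**5. Coverage.** With σ² = Var(S), approximate coverage is 2Φ(1.96 (S log S)²) − 1: 18.6% at S = 0.50 or 0.25, and 10.5% at S = 0.125. In 3,000 simulated Kaplan-Meier arms per case (n = 184, Greenwood variance, planned censoring) at 6, 12 and 18 months, the results were:

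- As stated, σ² = Var(S): 17.7%, 19.9% and 10.8% in Group A; 12.3%, 23.8% and 16.3% in Group B.
- As stated, Greenwood sum: 24.0% to 71.5%.
- Dividing: 94.1% to 95.1%.

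**The case against.** **It may not be on the page.** The text was read from a PDF by a program, and one lost slash or fraction bar would turn a correct formula into this one. The named method, the quantity τ² is said to be, and the interval expression are all right, which fits an extraction loss as well as an author's slip. This stands: the text alone cannot settle it.

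**The intervals come from software.** SAP 7.2.6 says they will be extracted from the PROC LIFETEST output data set. Nothing says they will be programmed by hand from the formula, and the software computes its own variance. This largely stands, and it is the main reason for a lower severity. It is not a full cure. The code is a sample subordinate to the methods section. It uses the life-table method, although 4.9.1 estimates the median in the same summary by Kaplan-Meier, and it names no log-log option. Its grid steps by 6 months, so it would not yield the 3-month interval its own note mentions. The mock-up programming notes mentioned in 7.2.6 are not among the documents and may say more.

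**It touches no test.** A reader might infer that chance differences between arms would look decisive. The documents do not support that. SAP 4.9.1 evaluates the treatment difference by the stratified log-rank test and estimates it by a stratified Cox hazard ratio, and neither uses τ. The OS-rate intervals are per-arm summaries outside the testing sequence in 4.9.

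**Conclusion.** As the text reads, the variance line in SAP 4.9.1 is wrong in direction under either usual meaning of σ², and σ² needs a definition in any case.

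Coded literally with σ² = Var(S), the OS-rate intervals would be about 7 to 15 times too narrow at 6 to 18 months. With σ² as the Greenwood sum, the factor is about 1.8 to 6.5 at 6 to 24 months. These figures rest on exponential survival at the planning medians. The tabulated intervals also assume 184 per arm and no censoring before t.

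A reader might infer one multiplier, such as 8 to 15, for every interval. That does not hold: the ratio varies with S, falls to 7.4 for Group B at 12 months, reaches 33 for Group A at 24 months, and depends on the undefined σ². Nor do the documents show that the reported intervals will be wrong, since they are planned from software output.

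The primary test, the hazard ratio and the power are unaffected. Severity is minor to moderate, and confidence is moderate because a division sign may have been lost in reading the PDF.

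**What to change.** 1. Check the source page of SAP 4.9.1 for a division sign.
2. If there is none, replace the line with τ²(t) = σ²(t)/[S(t) log S(t)]².
3. In either case, define σ²(t) as the Greenwood variance of S(t).
4. Align the sample code in 7.2.6 with the text: Kaplan-Meier method instead of method=lt, an explicit log-log interval option, and the same time points in the text, the code and the note.

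The cost is one formula line with a definition and a small edit to the sample code. Data collection, sample size, testing and trial conduct do not change.

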4.9.2 Progression-Free Survival (PFS)

PFS is defined as the time from the date of randomization to the date of first documentation of tumor progression or death from any cause, whichever occurs first. Tumor response assessments will be performed using Response Evaluation Criteria In Solid Tumors (RECIST) version 1.1.

PFS will be evaluated using the stratified log-rank test, as described for OS, with specific conventions for censoring. PFS data will be censored on the date of the last tumor assessment documenting absence of PD for subjects who 1) are given anti-tumor treatment other than the study treatment prior to observing objective tumor progression; 2) are removed from the study prior to documentation of objective tumor progression; 3) are ongoing and do not have objective tumor progression at the time of the analysis. Death or disease progression that occurs after more than one missed visit (i.e., 12 weeks) will be censored on the date of the last tumor assessment prior to the first missed visit. Subjects with no post-baseline tumor assessments will be censored on the date of randomization.

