8.1. Screening

Written informed consent must be obtained before any protocol-specific screening tests or procedures may be conducted. The screening period for a particular subject commences when the subject undergoes the first study-specific screening assessment. After informed consent is obtained, the following screening assessments will be performed within 21 days before the planned day of enrollment (Part 1) or randomization (Part 2) unless otherwise stated. Laboratory tests for eligibility will be performed at a central laboratory. Local hematology and chemistry laboratory results cannot be used to confirm eligibility. CT, or magnetic resonance imaging (MRI) if judged clinically appropriate, performed (as described in the protocol) prior to informed consent may be used if within 28 days prior to enrollment (Part 1) or randomization (Part 2). The method selected (CT or MRI) must be used consistently throughout the study.

General

- Demographics.
- Medical history (including prior treatment for SCLC, prior surgery, history of tobacco use and other significant medical conditions).
- Physical examination (including review of systems, height, weight, body surface area [BSA] using a standard formula), and ECOG status.
- Neurologic assessment (Investigator's assessment at baseline of whether the subject's mental status, coordination and gait, sensory function, motor function and vision [with consideration to corrective lenses as prescribed] are within the subject's normal limits.).

- Ophthalmology examination (including assessment of any vision problems and associated corrective measures, of pupils [size, shape, symmetry, response] and of any complaints regarding photophobia). The ophthalmology examination at screening is to be performed as part of the screening physical exam by the Investigator. The screening ophthalmology examination does not need to be performed by an ophthalmologist. However, if clinically significant deterioration in vision is noted during the course of the study, an ophthalmologist must be consulted, per [Section 6.7.8](#).
- Pain assessment (any pre-existing pain including locations and severity using the numeric 0-10 pain scale [[Appendix A](#)]).
- 12-lead electrocardiogram (ECG).
- Vital signs (systolic and diastolic blood pressure, respiration, pulse, and oral temperature).
- All ongoing medications.

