The time points for post dose samples start from the end of the infusion (e.g., 24 hours post dose = 24 hours after infusion end). Serial PK blood draws will be repeated with the first dose change (reduction or escalation). A validated assay will be used to measure concentration of dinutuximab. Details regarding sampling time points and procedures can be found in the lab manual.

- Sparse blood samples for population PK analysis during Cycle 1 at 2 time points and during Cycle 3 at 6 time points (**Part 2 Group B only**):

| Time points | Cycle 1 | |
|-------------|--|--|
| | Pre-dose | Infusion end |
| Windows | Anytime prior to dosing on the day of dosing | Up to 10 minutes after the end of the infusion |

| Time points | Cycle 3 | | Post dose, hours (Day) | | | |
|-------------|--|--|------------------------|--------------|--------------|--|
| | Pre-dose | Infusion end | 24 (Day 2) | 192 (Day 8) | 360 (Day 15) | 528 (Day 22) before the next dose (Cycle 4, Day 1) |
| Windows | Anytime prior to dosing on the day of dosing | Up to 10 minutes after the end of the infusion | ± 30 minutes | ± 60 minutes | | Anytime prior to the next dose on the day of the next dose |

The time points for post dose samples start from the end of the infusion (e.g., 24 hours post dose = 24 hours after infusion end). Details regarding sampling time points and procedures can be found in the lab manual.

- Blood samples for the evaluation of ADA and NAb in plasma pre-dose on Day 1 of all cycles plus Day 8 (+/- 1 day) and Day 15 (+/- 1 day) of Cycle 1 (**Part 1 and Part 2 Group B only**). Details regarding sampling time points and procedures can be found in the lab manual.
- Blood sample for biomarker analysis.
- Blood sample on Day 1 of every cycle to analyze CTC (**Part 2, selected regions only**).
- Disease assessments (CT or MRI of the chest/abdomen with contrast, with careful attention to the liver and adrenal and other locations as clinically indicated) every 6 weeks (+/- 7-day window) from the date of enrollment (Part 1) or randomization (Part 2).*

*Note: For subjects enrolled in Part 2, the timing of disease assessments should not be altered, even in the event of a dose delay or interruption in a cycle. This is very important to prevent or minimize evaluation-time bias.

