10.9.2. PFS

PFS will be defined as the time from the date of randomization to the date of first documentation of tumor progression or death from any cause, whichever occurs first. Tumor response assessments will be performed using RECIST version 1.1 ([Appendix C](#)).

PFS will be evaluated using the stratified log-rank test, as described for OS, with specific conventions for censoring. PFS data will be censored on the date of the last tumor assessment documenting absence of PD for subjects who 1) are given anti-tumor treatment other than the study treatment prior to observing objective tumor progression; 2) are removed from the study prior to documentation of RECIST confirmed tumor progression; 3) are ongoing and do not have objective tumor progression at the time of the analysis.

Subjects with no post-baseline tumor assessments will be censored on the date of randomization. Death or disease progression that occurs after more than one missed visit will be censored on the day following the date of the last tumor assessment.

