Target lesions. All measurable lesions up to a maximum of 2 lesions per organ and 5 lesions in total, representative of all involved organs, should be identified as target lesions and recorded and measured at baseline. Target lesions should be selected on the basis of their size (lesions with the longest diameter), be representative of all involved organs, but in addition should be those that lend themselves to reproducible repeated measurements. It may be the case that, on occasion, the largest lesion does not lend itself to reproducible measurement in which circumstance the next

largest lesion which can be measured reproducibly should be selected. A sum of the diameters (longest for non-nodal lesions, short axis for nodal lesions) for all target lesions will be calculated and reported as the baseline sum diameters. If lymph nodes are to be included in the sum, then only the short axis is added into the sum. The baseline sum diameters will be used as reference to further characterize any objective tumor regression in the measurable dimension of the disease.

Non-target lesions. All other lesions (or sites of disease) including any measurable lesions over and above the 5 target lesions should be identified as non-target lesions and should also be recorded at baseline. Measurements of these lesions are not required, but the presence, absence, or in rare cases unequivocal progression of each should be noted throughout follow up.

3. Methods for Evaluation of Disease

All measurements should be taken and recorded in metric notation using a ruler, calipers, or a digital measurement tool. All baseline evaluations should be performed as closely as possible to the beginning of treatment and never more than 4 weeks before randomization.

The same method of assessment and the same technique should be used to characterize each identified and reported lesion at baseline and during follow-up.

Clinical lesions. Clinical lesions will only be considered measurable when they are superficial (e.g., skin nodules and palpable lymph nodes) and ≥ 10 mm in diameter as assessed using calipers (e.g., skin nodules). In the case of skin lesions, documentation by color photography, including a ruler to estimate the size of the lesion, is recommended.

Chest x-ray. Lesions on chest x-ray are acceptable as measurable lesions when they are clearly defined and surrounded by aerated lung; however, CT is preferable.

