4.9.5 Other Efficacy Outcomes

Treatment groups will also be compared on the basis of the following additional efficacy outcomes, with tumor response defined by RECIST criteria (version 1.1):

Best Overall Response (BOR)

The BOR is the best response observed from the start of study treatment until the last assessment of tumor response recorded during follow-up or the start of any post treatment cancer therapy (whichever is sooner), taking into account any requirement for confirmation (i.e., at least 4 weeks apart). The number and percentage of subjects in each BOR category (i.e., CR, PR, SD, PD, and unevaluable) will be summarized by treatment group. Subjects with unconfirmed CR or PR assessments will be categorized separately. The table will include a category for subjects who died or discontinued the study due to disease progression prior to the first tumor assessment, as well as ongoing subjects without a tumor assessment prior to the data cut-off date for analysis. Subjects will be classified as having stable disease if assessed as SD (or better) at least 6 weeks after first dose date.

Data listings will display target lesion measurements and non-target lesion response assessments at each timepoint, together with the level of tumor response assigned by the investigator.

Time to Response (TTR)

The TTR is defined as the time interval between the date of randomization and the date of first documented CR or PR. CR or PR requires confirmation at least 4 weeks apart. Once it is confirmed, the first documented CR or PR will be considered as the start of the response. TTR will be descriptively summarized for subjects who responded.

Duration of response (DOR)

The DOR is defined as the time interval between the date of first documented PR or CR and the subsequent first date of disease progression as determined by radiological assessment using RECIST criteria (version 1.1) or death.

Subjects who do not experience disease progression and have not died will be censored on the date of their last tumor assessment. Disease progression that occurs after more than one missed visit (i.e., 12 weeks) will be censored on the date of the last tumor assessment prior to the first

missed visit. For OS, the death date will be used as an event time, no matter how many prior visits were missed.

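### The PFS missed-visit rule in SAP 4.9.2 equates two thresholds that differ for scan-detected progression, gives the 12 weeks no starting point, and can set a censoring date before randomization

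*SAP*

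**What the plan says.** - **Trigger.** SAP 4.9.2 reads "Death or disease progression that occurs after more than one missed visit (i.e., 12 weeks) will be censored on the date". It does not say when the 12 weeks begin.
- **Censoring date.** The subject is censored at the "date of the last tumor assessment prior to the first missed visit".
- **Fallback.** "Subjects with no post-baseline tumor assessments will be censored on the date of randomization".
- **Scan schedule.** Protocol 8.3 calls for disease assessments "every 6 weeks (+/- 7-day window) from the date of enrollment (Part 1) or randomization (Part 2"). Because the schedule is anchored to randomization, timing deviations do not accumulate.
- **Baseline scan.** Protocol 8.1 accepts a scan made before consent if it "may be used if within 28 days prior to enrollment (Part 1) or randomization (Part 2"). Protocol Appendix C sets the same limit: "never more than 4 weeks before randomization".
- **Protocol rule.** Protocol 10.9.2 uses the visit count alone, with no week equivalent. An event "after more than one missed visit will be censored on the day following the date of the last tumor assessment".
- **Duration of response.** SAP 4.9.5 repeats the gloss, but for progression only: "Disease progression that occurs after more than one missed visit (i.e., 12 weeks) will be censored". Death also ends DOR under its definition there, yet the DOR missed-visit rule does not mention it.
- **Precedence.** SAP section 1 says the SAP overrides the protocol and will flag substantial differences. SAP 3.1 lists no changes.

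**The concern.** The SAP offers the visit count and the 12 weeks as the same thing. On a 6-week schedule, 12 weeks is what separates two scans when just one between them is missed. A programmer who counts missed visits and one who codes 84 days since the last scan would produce different lists of PFS events, and each could point to the text.

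PFS is the first endpoint tested after OS in the hierarchy of SAP 4.9. Censoring a progression back at the last scan before the miss removes an observed event. The trial is open-label, and Protocol 8.3 and 8.4 themselves warn of evaluation-time bias and informative censoring. The PFS tables listed in SAP 8.1 vary only the population (ITT, mITT), so no planned output would show whether the reading matters.

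A second, separate flaw lies in the censoring date. For a subject whose first post-baseline scans are the missed ones, the last assessment before the first miss is the baseline scan, which precedes randomization.

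**Working it through.** **Inputs.** Interval 6 weeks = 42 days and window of 7 days either side (Protocol 8.3); baseline scan up to 28 days before randomization (Protocol 8.1); threshold 12 weeks = 84 days (SAP 4.9.2). The distribution of scan days within the window is not in the documents and is assumed below.

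**1. Where 12 weeks comes from.** Two missed visits x 6 weeks = 12 weeks. Measured from an on-schedule scan, this is the day the second missed scan falls due. The figure reproduces in that sense.

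**2. Gap between the last scan and the scan that shows progression.** Nominal gap = 42 x (missed scans + 1) days. Each of the two scans can move by 7 days, so the range is the nominal gap plus or minus 14 days.

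| Missed scans | Nominal gap | Range |
|---|---|---|
| 1 | 84 days (12 weeks) | 70 to 98 days |
| 2 | 126 days (18 weeks) | 112 to 140 days |

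The ranges do not overlap. An 84-day limit falls in the middle of the single-miss range.

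**3. Share of single-miss progressions censored.** The gap is 84 + a - b, where a and b are the window offsets (-7 to +7) of the later and earlier scan. There are 15 x 15 = 225 combinations: 15 equal 84 days exactly, and (225 - 15)/2 = 105 exceed it.

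| Reading or timing | Share censored |
|---|---|
| Visit count | 0% |
| More than 84 days, uniform | 105/225 = 46.7% |
| 84 days or more, uniform | 120/225 = 53.3% |
| More than 91 days (one window added), uniform | 28/225 = 12.4% |
| More than 84 days, later scan always early / always late | 23% / 70% |
| More than 84 days, all scans on the due day | 0% (100% if 84 days or more) |
| More than 84 days, extremes (earlier scan late and later scan early / the reverse) | 0% / 98% |

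If the week-6 scan is missed, progression is found at week 12 and the clock runs from a baseline scan uniform over 1 to 28 days before randomization, 392 of 420 combinations (93%) exceed 84 days. If the clock runs from randomization, 7/15 = 46.7% do.

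**4. Share of all PFS events (illustration).** The documents give neither median PFS nor a missed-scan rate. Assuming a median of 2.5 to 4 months, 15% of events being deaths and 5 to 10% of scans missed at random, simulation puts the share censored at about 4 to 10% under the 84-day reading and about 0.5 to 2% under the visit count.

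**5. Deaths.** With the last scan on day 42, the missed scans fall due on days 84 and 126. Day 126 is 84 days after the last scan, so the thresholds nominally agree. If a visit counts as missed once its window closes (day 133), the gap at that point is 133 - 42 = 91 days, or 84 to 98 days as the last scan moves within its window.

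**6. Censoring date.** Suppose weeks 6 and 12 are missed and week 18 shows progression. The visit count triggers censoring, and the last assessment before the first miss is the baseline scan. The week-18 scan is a post-baseline assessment, so the randomization fallback does not literally apply. PFS time is then zero or negative by up to 28 days. Under the 84-day reading, missing week 6 alone can produce the same result. A subject censored at or before time zero is in no risk set, so moving the date to randomization leaves the log-rank statistic unchanged.

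**The case against.** The strongest reply is that the visit count is the operative wording and the 12 weeks only illustrates it. The protocol uses the visit count alone, the SAP declares no change from the protocol, and 2 x 6 = 12 is a natural gloss for two missed visits. On that reading no single-miss progression is censored.

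This limits the claim but does not remove the problem. The SAP governs, it adds a number the protocol lacks, and for scan-detected progression that number describes the other case.

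Three stronger readings are tempting, and the documents do not support them:

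- *That about half of progressions after one missed scan are wrongly censored.* This requires the gloss to override the visit count, the clock to start at the last scan, and scan timing to be roughly symmetric in the window. The SAP settles none of these.
- *That pre-randomization dates result from the threshold mismatch, or move the PFS p-value.* They come from the censoring-date wording and arise under either threshold. Correcting the date itself leaves the test unchanged.
- *That one arm is favoured.* Missed scans may differ by arm in an open-label trial, but nothing in the documents shows that they will, and no effect on the hazard ratio was computed.

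The DOR inconsistency is real but minor: DOR is summarized descriptively and lies outside the testing hierarchy.

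**Conclusion.** The point stands as an ambiguity in the governing rule for PFS. For scan-detected progression the two stated thresholds select different events: 112 to 140 days for two missed scans, against 12 weeks, the nominal gap after one (70 to 98 days). The 47% figure is the consequence of one possible coding with uniform scan timing; across readings and timing patterns the share runs from 0% to nearly 100%. The share of all PFS events at stake depends on median PFS and missed-scan rates that the documents do not give.

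The pre-randomization censoring date is a separate error of validity, confined to subjects who miss their first post-baseline scan or scans.

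OS is not affected: SAP 4.9.5 counts a death as an OS event however many visits were missed. This should be corrected before the data are locked, but it does not threaten the primary analysis.

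**What to change.** 1. **Threshold.** Delete the 12-week parenthesis in SAP 4.9.2 and 4.9.5. Censor when two or more consecutive scheduled assessments (6-week visits, plus or minus 7 days, from randomization) were missed immediately before the progression or death.
2. **Progression.** For in-window scans this equals more than 98 days since the last adequate assessment, or since randomization if there is no post-baseline one. The longest single-miss gap is 98 days and the shortest double-miss gap is 112 days. From randomization, the week-12 scan falls at days 77 to 91 and the week-18 scan at days 119 to 133.
3. **Deaths.** Count a visit as missed once its window has closed. Do not apply the 98-day limit to deaths. With the last scan on day 42, the scans due on days 84 and 126 missed, and death on day 135, two visits are missed but the gap is only 93 days, so that limit would keep the event.
4. **Censoring date.** Use the later of randomization and the last adequate assessment before the first missed visit.
5. **DOR.** Apply the same rule to progression and death alike.

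Cost: SAP wording only, before database lock. No new data are needed and the primary analysis does not change.
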